15.1 Appendix 1: Nosebleed monitoring sheet

RENDU-OSLER : FICHE DE SURVEILLANCE DES EPISTAXIS

Nom : Prénom : Né(e) le :

ANNEE : 20

Incrire dans la colonne correspondant au jour du mois, la durée en minutes de chaque épistaxis.

MOIS :

Jour	1	2	3	4	5	6	7	8	9	10	11	12	13	14	15	16	17	18	19	20	21	22	23	24	25	26	27	28	29	30	31
Episode 1																															
Episode 2																															
Episode 3																															
Episode 4																															
Episode 5																															
Episode 6																															
Episode 7																															
Episode 8																															
Total																															

ADMINISTRATION DE LA POMMADE PROTOPIC OU PLACEBO. FAIRE UNE CROIX TOUS LES JOURS POUR CHAQUE ADMINISTRATION																															
Jour	1	2	3	4	5	6	7	8	9	10	11	12	13	14	15	16	17	18	19	20	21	22	23	24	25	26	27	28	29	30	31
Matin																															
Soir																															

Jour	1	2	3	4	5	6	7	8	9	10	11	12	13	14	15	16	17	18	19	20	21	22	23	24	25	26	27	28	29	30	31
Transfusion																															
Nb CGR																															
Injection Fer IV (mg)																															
Hemoglobine																															

Noter la liste des événements que vous jugez importants survenus pendant cette période, la date de début et de fin, la prise d'autres traitements :

Date :	Commentaire :

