4.4 Randomization, blinding and lifting the blind

The randomization process will be centralized. Allocation of a randomization arm to a patient included will be made by IWRS (Interactive Web Response System), on the basis of a unique randomization list for all investigation centers.

The lists of randomization will be pre-established, by the “Pole IMER” at the Hospices Civils de Lyon – Clinical Research Unit.

Clinsight (Ennov clinical) software will be used to manage this study.

During the inclusion visit, after verifying the inclusion criteria, the investigator connects to the platform to include the patients in the eCRF. This will assign an identification number. When inclusion is validated, the patient is randomized and a treatment code is allocated by the system. The treatment is then dispensed by the pharmacy at the Hospital Center.

This will be a double blind study in which neither the patient nor the investigator will be aware of the nature of the treatment administered so as to annul any bias in the follow-up and measurements.

Tubes of Tacrolimus 0.1% or placebo will be identical and will have appropriate labeling.

Should a serious adverse event occur, the main investigator, the co-investigators or the sponsor may request that the Anti-Poison Center in Lyon lift the blind 24h/24h (the phone number is written on the clinical trial participation card). The written detailed procedures for lifting the blind will be given to the investigators and the Anti-Poison Center in Lyon.

All requests for unblinding must be justified. Most often, study drug discontinuation and knowledge of the possible treatment assignments are enough to treat a study patient who presents with an emergency condition. When the investigator asks for unblinding, he/she must provide patient identifying information, the date, and the reason for unblinding. The investigator will be informed of the details of the drug treatment.

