6.2 Inclusion visit (V1)

Patients will be seen at a consultation for the treatment by a doctor and a clinical research assistant from the center if possible.

At this visit:

- The investigator will once again inform the patients about the study.
- The nosebleed grids completed by the patient in the 6 weeks prior to the treatment will be collected (Appendix 1: Nosebleed monitoring grid).
- The inclusion and exclusion criteria will be verified and the consent form will be signed. The investigator connects to the platform, includes the patient and an identification number will be assigned to the patient.
- The patient will undergo a clinical examination, including blood pressure and heart rate.
- A urinary pregnancy test will be performed for all female patients of child-bearing age. The investigator will inform these patients that there is no data available in pregnant women and they must use an effective contraceptive method (combined hormonal contraceptive, implant, intra-uterine device). The use of any other means, such as condom, will be left to the judgment of the investigator; the patient will have to give her commitment which will be recorded in the medical file.
- The number of red blood cell transfusions in the 6 weeks prior to administration of the treatment will be noted (as noted by the patient on the nosebleed grids).
- Any concomitant treatments will be noted.

If all the criteria are validated:

- The examination will be completed by a set of biological blood samples (2 x 5 mL tubes) for hemoglobinemia and serum ferritin.

- An ENT examination will be carried out (Appendix 3: Monitoring ENT examination).
- The ESS questionnaire is completed by patient (Appendix 2).
- An SF36 quality of life questionnaire will be given to the patient for completion.
- The nosebleed grids will be given to the patient for ENT monitoring during the 6 weeks of treatment (Appendix 1: Nosebleed monitoring grid). Specific boxes are provided to mark the two daily administrations, in order to verify observance of the treatment. If convenient for the patient a connexion code can be provided to allow them to complete these grids online on eCRF.

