9.2.2.6 Handling of missing values/censoring/discontinuations

Follow-up of patients will be pursued regardless of the situation, except if the patient withdraws his or her consent. In the case of nasal surgery during the study period or any other treatment that is a substitute to the studied treatment, the patient will be followed up but his or her results will be considered as a failure.

The main judgement criterion is based on grids that are filled in daily. Patients are used to these grids and fill them in carefully; the daily durations are summarized over 6 weeks. However if one day is missing, the value will be replaced by an average of the 4 values before and the 4 values after the missing value. This strategy will be applied up to 7 missing values over 6 weeks (i.e. 10%).

If more than 7 days and less than 21 days (included) are missing, a daily average will be computed from the data available (from the 6-week period evaluated) and will be multiplied by 42 to obtain the overall estimated duration.

If a patient is lost to follow-up or refuses to communicate his nosebleed grids or has more than 21 days missing on his grids, the result for the concerned patient will be considered as a failure.

10 Quality assurance

The Clinical research associate mandated by the sponsor is responsible for inspecting the case report forms in conformity with the monitoring schedule for the study, throughout the study, verifying that the protocol is being respected, as well as the totality and the conformity of the source documents, the coherence of the data and that the regulations governing good clinical practices are being respected. The Clinical research associate mandated must have access to the medical files of the patients and other files in relation to the study needed to verify the data entered in the study's electronic case report forms.

The controls of presence, verisimilitude, and coherence will be carried out electronically in accordance with the rules defined in advance. Requests for information will be generated when possible errors are detected.

The health authorities and/or an independent auditor mandated by the sponsor may audit any investigation site, or the sponsor, throughout the duration of the study or after the end of the study so as to control how the study is being conducted and the quality of the data. The investigator must provide direct access to the source documents, and the sponsor to the regulatory documents.

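### The nosebleed grid gives no way to mark a bleed-free day, so in both primary-endpoint windows a blank column may be a zero or a missing day, and the missing-day rules need to know which

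*Combined protocol and SAP*

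**What the plan says.** Appendix 1 (15.1) is a monthly sheet with eight Episode rows and a Total row for each day. Its bleeding instruction is "Incrire dans la colonne correspondant au jour du mois, la durée en minutes de chaque épistaxis". There is no request to write 0 and no box for a day without bleeding. The only mark the sheet asks for every day is the ointment cross ("FAIRE UNE CROIX TOUS LES JOURS POUR CHAQUE ADMINISTRATION"), which applies only while the patient is being treated.

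The primary endpoint (4.3.1, 9.2.2.4) compares total bleeding time in the 6 weeks after treatment with the 6 weeks before. No cross is due in either window.

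Two sets of rules count missing days:

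- The synopsis and 4.2.5 exclude a patient with more than 7 missing baseline days, labelled as 10%.
- Section 9.2.2.6 has three tiers. Up to 7 missing days (again labelled 10%) are each replaced by the mean of the 4 values before and the 4 after. For 8 to 21 missing days, the mean of the available days "will be multiplied by 42 to obtain the overall estimated duration". More than 21 is a failure.

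On completion, 6.1 describes the grid as filled in daily and 9.2.2.6 states "Patients are used to these grids and fill them in carefully". Grids are collected in person at V1, V2 and V3. Section 8.1 asks for an explanation of missing data, and section 10 plans presence checks: "Requests for information will be generated when possible errors are detected".

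Online entry is optional and is offered at V1 (6.2): "If convenient for the patient a connexion code can be provided to allow them to complete these grids online on eCRF".

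**The concern.** A patient who follows the form as printed leaves a bleed-free day blank. A patient who forgets the form also leaves it blank. Such days should be common: about 30 minutes of bleeding in 6 weeks is enough to qualify (synopsis, 4.2.4). Outside the treatment period nothing else on the sheet shows whether the day was attended to, so the analyst cannot recover the difference from the grid.

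The baseline window is the more exposed. The online code is offered at V1, so as described the baseline grid is on paper for every patient. Eligibility, including the missing-day count, is settled before electronic entry (4.4): "after verifying the inclusion criteria, the investigator connects to the platform to include the patients in the eCRF".

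At stake is a yes/no classification at a 30% cut-off in 48 patients. Unfilled days read as 0 lower one of the two totals. At follow-up this can create a false responder; at baseline it can hide a true one. Bleed-free days read as missing push a total up, or make the patient a failure by rule.

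**Working it through.** **The plan's own percentage.** The limit is 7 days in a 42-day window: 7/42 = 16.7%, not 10%. Ten per cent of 42 is 4.2 days. The day count is what operates, so this is a labelling error.

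**Inputs.** 42-day windows, a 30% reduction as the responder threshold (taken as 30% or more), and the 9.2.2.6 tiers. Assumptions: equal minutes on each bleeding day, and the other window fully and correctly recorded. The number of unfilled days k is not in the documents and is varied.

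**A. Blanks read as 0, patient bleeds every day.**

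Follow-up unfilled, true reduction r: apparent reduction = 1 − (1 − r)(42 − k)/42.

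| True reduction | k | Apparent reduction |
|---|---|---|
| 0% | 12 | 28.6% |
| 0% | 13 | 31.0% (false responder) |
| 10% | 10 | 1 − 0.90 × 32/42 = 31.4% (false responder) |
| 20% | 6 | 1 − 0.80 × 36/42 = 31.4% (false responder) |
| 25% | 3 | 1 − 0.75 × 39/42 = 30.4% (false responder) |

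Baseline unfilled: apparent reduction = 1 − (1 − r) × 42/(42 − k). All cases below stay within the 7-day limit.

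| True reduction | k | Apparent reduction |
|---|---|---|
| 33% (42 to 28 days) | 3 | 1 − 28/39 = 28.2% (responder lost) |
| 35% | 4 | 1 − 0.65 × 42/38 = 28.2% (responder lost) |
| 40% | 7 | 1 − 0.60 × 42/35 = 28.0% (responder lost) |
| 45% | 7 | 1 − 0.55 × 42/35 = 34.0% (still a responder) |

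In each of these cases, recognising the days as missing and applying 9.2.2.6 returns the true reduction.

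**B. Blanks read as 0, intermittent bleeder.** With n bleeding days among 42 and k days unfilled at random, the number of bleeding days lost is hypergeometric.

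- Follow-up, no true change. The patient becomes a false responder if at least 0.30n bleeding days are lost (5, 7 and 9 for n = 14, 21 and 28). With k = 13 the probability is 45%, 50% and 55%. With k = 6 it is 1.1%, 0% and 0%.
- Baseline, true 40% reduction, k = 7. The patient is lost as a responder if 1 − 0.6n/(n − lost) falls below 0.30, that is, if more than n/7 bleeding days are lost (at least 3, 4 and 5). The probability is 43%, 50% and 57%.

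**C. Blanks read as missing.** Ten true bleed-free days left blank fall in the 8-to-21 tier, so the total is multiplied by 42/32 = 1.31. If this happens at follow-up, a true 40% reduction appears as 1 − 0.60 × 42/32 = 21%. More than 21 bleed-free blanks make a well-controlled patient a failure. At baseline, more than 7 exclude an otherwise eligible patient.

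**The case against.** The best case against the point is that the plan treats every day as either having a value or being missing. The grid is described as completed daily, the Total row has a cell for each day, and patients may write 0 there unprompted. No section tells staff to read a blank as 0. Forms are handed over in person, missing data must be explained and queries are planned. User guides and training (8.4) may carry a convention that is not visible here, and the online grid is not shown. For a daily bleeder a blank column is conspicuous and likely to be queried. For an intermittent bleeder, 6 unfilled follow-up days almost never create a false responder when there is no true change.

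Much of this stands. The safeguards lower the risk, and the finding is limited to what these documents state. They do not close the gap, because a blank must be recognised as missing before it is explained or queried, and none of them says how to recognise it. By the visit the day in question may be weeks old: from day 43 to the latest tolerated V3 at day 100 is 57 days. Intermittent bleeders are not safe at baseline either, as the 43% to 57% in part B shows.

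A reader might infer that blanks will in practice be scored as 0, that the result is therefore biased towards one arm, or that power falls by a calculable amount. The documents support none of these. How blanks are read is not stated, and the opposite reading distorts in the other direction. The trial is double-blind, so a uniform reading does not by itself favour an arm when the treatment has no effect. Any power figure would need an assumed change in response rates that the plan does not give.

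**Conclusion.** The point holds as a gap in the definition of the primary data. The form gives no way to mark a bleed-free day, the plan does not define a missing day, and both the eligibility limit and the tiers in 9.2.2.6 depend on counting such days. Information lost this way cannot be recovered at analysis.

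The size is shown for single patients only. Between 3 and 13 unfilled follow-up days, or 3 to 7 unfilled baseline days, move a daily bleeder across the 30% line if blanks are read as 0. Ten bleed-free days inflate a total by 31% if blanks are read as missing. These results rest on equal minutes per bleeding day, a correct other window and, in part B, days unfilled at random. They are not frequencies.

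It should be corrected because the remedy is cheap and the endpoint is a single threshold in a small trial. The 10% label is a separate, minor error.

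**What to change.** 1. On the paper and online grids, for all three periods, print an instruction to write 0 in the Total row on a day without a nosebleed.
2. At V1, V2 and V3, go through blank columns with the patient and record each as 0 or as missing before missing days are counted.
3. In 4.2.5 and 9.2.2.6, define a missing day as one with no Episode or Total entry that is still unresolved after that review. Without the review, a rule that no entry means missing would penalise patients who go on leaving bleed-free days blank.
4. Separately, correct 10% to 16.7% in the synopsis, 4.2.5 and 9.2.2.6, or reconcile the day count if 10% (about 4 days) was intended.

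The cost is one printed line, the same instruction online, a short check at visits already planned, one definition used in two sections and three corrected percentages. The downsides are a small daily burden for patients, reliance on recall for days several weeks back, and a residual risk that unresolved bleed-free blanks are treated as missing.

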4.3.2 Secondary judgement criteria

1. Adverse Events (AE) and Severe Adverse Events (SAE) observed throughout the study (clinical examination, epistaxis grids, ENT examination at each visit before and after the treatment). Additionally, all patients are contacted by phone after 15 and 30 days of treatment in order to collect data on tolerance and observance of the treatment.
2. Clinical efficacy criteria:
 - Nosebleed duration will be evaluated by the nosebleed monitoring grids completed by the patient (Appendix 1), collected at inclusion (V1): observation of the nosebleeds in the 6 weeks prior to inclusion, at the end of the treatment (V2): observation of the nosebleeds in the 6 weeks during treatment, and at the end of the study (V3): observation of the nosebleeds in the 6 weeks after the end of the treatment.
 - Progress in the number of nosebleeds. This criterion will be evaluated by the nosebleed monitoring grids completed by the patient (Appendix 1) collected at inclusion (V1): observation of the nosebleeds in the 6 weeks prior to inclusion, at the end of the treatment (V2): observation of the nosebleeds in the 6 weeks during treatment, and at the end of the study (V3): observation of the nosebleeds in the 6 weeks after the end of the treatment.
 - Comparison of the number of red blood cell transfusions between inclusion (V1) (collected over 6 weeks before treatment), the end of the treatment (V2) (collected over 6 weeks of treatment) and at the end of the study (V3) (collected over 6 weeks after the end of the treatment).
 - Progress in the scores obtained in the SF36 quality of life questionnaire

completed at inclusion (V1), at the end of the treatment (V2) and at the end of the study (V3).

- Progress in the ESS (Epistaxis Severity Score) using data from the specific questionnaire (Appendix 2) completed at inclusion (V1), at the end of the treatment (V2) and at the end of the study (V3).

Biological efficacy criteria: progress in hemoglobin and serum ferritin concentrations between inclusion (V1) and the end of the treatment (V2) and at the end of the study (V3).

3. Systemic absorption, after 1, 3 and 6 weeks of nasal administration, will be evaluated by a tacrolimus dosage in the blood at the end of the treatment.

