6.2.2 Recommendations

Patients will receive recommendations on how to contact the doctor in case of the onset of adverse events.

A burning sensation is frequently observed at the administration site; usually this sensation is acceptable and disappears after a few days of administration.

In case of an adverse event probably due to the product: skin irritation, an unacceptable burning sensation, pruritus, and erythema, at the application site:

- The patient must stop the treatment.
- He or she must inform the investigator as soon as possible.
- Based on symptoms, a medical consultation can be carried out by a general practitioner, a specialist or an investigator involved in the study.
- The treatment can be reintroduced, or not, after clinical normalization.
- It is up to the investigator to make the decision in the interest of the patient, on the basis of the balance between the risk of a new event and the risk of aggravation of the disease.

The modalities for managing nosebleeds will be given to the patients to inform all doctors of the treatment of the nosebleeds specific to this disease.

6.3 Phone calls on day 15, 14 days after the beginning of the treatment (up to day 18 tolerated)

Patients will be contacted by phone, 14 days after the beginning of the treatment, to collect intermediate data regarding tolerance and observance.

The following data will be collected:

- Treatment observance: any interruption to the treatment interruption will be noted precisely (date, duration), as will the reason for the interruption.
- Occurrence of adverse events: nature, date of onset, and whether or not a symptomatic treatment was given.
- Any change in the concomitant treatments.
- The date of the blood sample planned at day 8 (FK506 dosage).

6.4 Phone calls on day 31, 30 days after the beginning of the treatment (up to day 37 tolerated)

Patients will be contacted by phone, 30 days after the beginning of the treatment, to collect intermediate data regarding tolerance and observance.

The following data will be collected:

- Treatment observance: any interruption to the treatment interruption will be noted precisely (date, duration), as will the reason for the interruption.
- Occurrence of adverse events: nature, date of onset, and whether or not a symptomatic treatment was given.
- Any change in the concomitant treatments.
- The date of the blood sample planned at day 22 (FK506 dosage).

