7.1.3 Intensity

The intensity of the event will be graded according to the following classification:

- Mild (grade 1): Discomfort noticed but no disruption of normal daily activity
- Moderate (grade 2): Discomfort sufficient to reduce or affect normal daily activity
- Severe (grade 3): Incapacitating with inability to work or perform normal daily activity
- Life-threatening (grade 4): Substantial risk of dying at time of event
- Death: (grade 5)

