7.2 Responsibilities of the investigator

7.2.1 Adverse Events reporting

All **adverse events (AE)** regardless of seriousness or relationship to Investigational Product that occurred **after the informed consent up to 30 days after the last study drug administration** are to be recorded in the AE pages of the Case Report Form (CRF). After this delay only fatal AE and adverse event related to the IMP must be recorded.

Whenever possible, symptoms should be grouped as a single syndrome or diagnosis. The investigator should specify the date of onset, intensity, action taken regarding trial medication, corrective therapy given, outcome of all adverse events and his opinion as to whether the adverse event can be related to the study drugs and/or to concomitant drugs.

All events that meet one or more criteria of seriousness will be reported as Serious Adverse Event.

7.2.2 General AE/SAE reporting rules:

Any episode of any grade of toxicities, related to a Serious Adverse Event must be reported as "Adverse Event" in the appropriate CRF pages.

Adverse events (serious or not) will not be recorded after the start of a new out-of-study treatment or after disease progression.

Planned hospital admissions or surgical procedures for an illness or disease which existed before the patient was enrolled in the study or before study drug was given are not to be considered SAEs unless the condition deteriorated in an unexpected manner during the study (eg surgery was performed earlier than planned).

All adverse events which meet grade 3, 4 and 5 criteria must be reported immediately to the sponsor.

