11.2 Benefit / risk ratio

All the surgical treatments currently on offer are aggressive for the nasal mucosa and present a risk of perforation of the nasal septum.

Patients' participation in this study will not compromise their possibility for future medical or surgical treatment.

The expected adverse events in this study are:

- Skin burning or irritation at the application site (approximately half of the patients). These symptoms are usually mild to moderate and generally go away within one week of using Protopic. Administration could be easily stopped in case of adverse reaction.
- The risk of systemic adverse events related to tacrolimus is low given the very low doses of tacrolimus administered to the patients. Tacrolimus in blood is monitored and the treatment will be stopped in case of absorption.
- Risk for the blood test may be of the hematoma type at the puncture point or fainting.

If the efficacy of the treatment is shown, the treatment will be proposed to all the patients who have received the placebo.

The risk / benefit ratio for a patient participating in this study is thus perfectly acceptable.

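### The nosebleed grid asks only for events the patient judges important, narrower than the all-events rule in 7.2.1, so mild first-week reactions may be missed

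*Combined protocol and SAP*

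**What the plan says.** Section 4.3.2 lists the sources for the adverse-event criterion as "clinical examination, epistaxis grids, ENT examination at each visit before and after the treatment". It then adds a further one: "Additionally, all patients are contacted by phone after 15 and 30 days of treatment in order to collect data on tolerance and observance".

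Section 7.2.1 sets the recording rule: all adverse events from consent to 30 days after the last dose, "regardless of seriousness or relationship to Investigational Product". Section 7.1.3 brings the mildest events into scope: "Mild (grade 1): Discomfort noticed but no disruption of normal daily activity".

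The grid in Appendix 1 is mainly a daily diary of nosebleed durations, ointment applications and transfusions. Below these is a comment box headed "Noter la liste des événements que vous jugez importants survenus pendant cette période", with a request for start and end dates and for other treatments taken.

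Section 11.2 expects burning or irritation at the application site in about half of patients and adds: "These symptoms are usually mild to moderate and generally go away within one week of using Protopic". The first scheduled question after treatment starts is in section 6.3: "Patients will be contacted by phone, 14 days after the beginning of the treatment, to collect intermediate data regarding tolerance and observance" (day 15, tolerated to day 18).

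Section 9.2.2.5 lists adverse events by frequency in each group and compares the percentage of patients with at least one, on the safety population.

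**The concern.** A form that feeds the adverse-event record should not be narrower than the rule for that record. Here the patient is asked to apply a threshold of importance that 7.2.1 does not contain.

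The mismatch matters most in the first week. The expected local reactions are mild and short, so they are the events a patient is least likely to call important, and they are usually over before anyone is scheduled to ask. Tolerance is the first secondary objective, and section 2.2 says that the safety of nasal tacrolimus ointment is unknown. If mild early reactions drop out of the record, the frequency table and the percentage with at least one event become less complete on the question the trial is meant to inform.

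**Working it through.** The plan gives no figure for adverse-event capture. Its one design figure, 22 per group for 60% v 15% with a two-sided 5% Fisher test, concerns the primary endpoint. It reproduces (exact power 82.7% at 22 per group, 79.9% at 21) and is not affected by this point.

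**1. Which sources cover the first treatment week?**
- Clinical and ENT examinations: V1, V2 and V3 (Table 1). V1 is before treatment and V2 is at day 43 to 50. The ENT form in Appendix 3 has no dedicated field for burning, itching or redness.
- Grid: filled in daily, so it covers the week as it happens, but its event box is limited to important events.
- Day 8 blood sample: taken at a laboratory the patient chooses (6.2). Table 1 schedules no adverse-event collection then.
- Calls at day 15 and day 31 (6.3, 6.4): ask about any adverse event, from recall.
- V2 and V3 (6.5, 6.6): collect any adverse event, from recall.
- Patient-initiated report (6.2.2): for irritation, unacceptable burning, itching or redness probably due to the product, the patient must inform the investigator as soon as possible.

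**2. How long must the patient remember?** For a reaction on days 1 to 7 and a call on days 15 to 18:
- shortest gap: 15 − 7 = 8 days
- longest gap: 18 − 1 = 17 days

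**3. How much could be lost?** This part rests on assumptions. If the grid catches a share g of mild reactions, and the calls and visits independently catch a share q, total capture is 1 − (1 − g)(1 − q). Taking q from 80% to 95% (assumed):
- g = 0: capture is 80% to 95%.
- g = 50%: 1 − 0.5 × 0.20 = 90%, up to 1 − 0.5 × 0.05 = 97.5%.

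**4. Can this become a loss of power?** Only with more assumptions: 24 per arm, a true rate of 50% on active, a placebo rate of 10%, 20% or 30%, and equal capture in both arms. Exact two-sided Fisher power is then:

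| Capture | Placebo 10% | Placebo 20% | Placebo 30% |
|---|---|---|---|
| 100% | 83% | 49% | 21% |
| 80% | 69% | 36% | 15% |
| 60% | 50% | 24% | 10% |

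At full capture, changing the assumed placebo rate alone moves power from 83% to 21%. The table illustrates how sensitive the comparison is; it does not estimate the effect of the grid's wording.

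**The case against.** The strongest reply is that the grid's box is a supplement. The same criterion in 4.3.2 goes on to the phone calls. Table 1 schedules adverse-event collection at five contacts, and none of them carries an importance filter. The recorded data are the adverse-event pages of the CRF, where the investigator specifies onset, intensity and relationship. Patients also receive a participation card with phone numbers and an instruction to report troublesome local reactions promptly. All of this stands, and it confines the gap mainly to tolerable, short-lived reactions that the patient neither writes down nor recalls.

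Three stronger readings are tempting, and the documents support none of them:

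- **That mild reactions are under-recorded, by a known amount.** No capture rate is given for any source, and a loss also requires failed recall at an unfiltered call.
- **That the difference between arms is understated.** This follows if capture is equally incomplete in both arms. An importance filter might instead remove trivial background events and leave the contrast unchanged or sharper. The direction is not established.
- **That the interval from V2 to V3 adds to the problem.** It is 35 to 57 days (85 − 50 and 100 − 43), but treatment is over by then, so it has little bearing on application-site reactions expected in the first week.

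The numerical rules for the DSMB in section 2.3 count treatment stops of at least 8 consecutive days, which this wording does not affect. The single date column in the box is a matter of layout, since the instruction already asks for both dates.

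**Conclusion.** The inconsistency is real: a named source of adverse events asks for less than 7.2.1 requires. Its consequence is a possibility: mild first-week reactions may be missed when they are neither noted nor remembered over 8 to 17 days. This assumes that patients follow the instruction literally and that reactions resolve on the timescale in 11.2. The size of the loss cannot be computed from the documents. No sample size, primary analysis or stopping figure changes. Severity is minor; the change is worth making because it costs almost nothing and serves the first secondary objective.

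**What to change.** In Appendix 1, replace the restriction to events the patient judges important with a request for all events, even mild or brief (for example *tous les événements, même légers ou passagers*), keeping the request for start and end dates. Make the same change to the online grid if it carries the same wording; its text is not in the documents. Have staff review the entries at the existing day 15 and day 31 calls and at V2 and V3, and have the day 15 call ask specifically about the first week.

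No visit or procedure is added. The cost is one revised patient sheet, possibly one online form, and more minor events to enter and code. Printed symptom prompts are not needed for this correction: they would move the grid from spontaneous towards solicited reporting and could raise rates in both arms, which is a separate choice for the sponsor.
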